## 2.5.1 Primary endpoint(s)

The primary efficacy variable is the change from BSL in the WORC PSD score at Week 16 in participants with moderate to severe RCT.

## 2.5.2 Statistical hypothesis, model, and method of analysis

WORC PSD change from baseline over time will be presented by treatment group using a summary table. Superiority testing will be omitted.

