3.1 Primary estimands

The primary scientific question of interest is: what is the effect of secukinumab 300 mg s.c. compared to placebo in participants with moderate to severe RCT in change from BSL in the WORC PSD score at Week 16 regardless of discontinuation due to any reason, use of prohibited medication, or use of rescue medication?

The primary estimand will be based on the following attributes:

- Population: defined through appropriate inclusion/exclusion criteria to reflect the targeted moderate to severe RCT population
- Endpoint: change from BSL in the WORC PSD score at Week 16

- Treatment of interest: the randomized treatment (secukinumab or placebo)
- Handling of remaining intercurrent events is the following:
 - 1. Discontinuation of study treatment due to any reason (including AE and lack of efficacy): if participants discontinue study treatment due to any reason (including AE and lack of efficacy), the event will be ignored (treatment policy)
 - 2. Prohibited medication: if participants receive prohibited medication without study treatment discontinuation, the event will be ignored (treatment policy)
 - 3. Rescue medication: if participants take rescue medication without study treatment discontinuation, the event will be ignored (treatment policy)
- Summary measure: difference in means between treatments.

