9.3.3 Statistical model, hypothesis, and method of analysis

The statistical hypothesis being tested is that there is no difference in the secukinumab 300 mg s.c. regimen versus placebo regimen in the mean change from BSL in the WORC PSD score at Week 16.

Let μ_0 denote mean change from BSL in the WORC PSD score at Week 16 for placebo regimen and μ_1 denote the mean change from BSL in the WORC PSD score at Week 16 for secukinumab 300 mg s.c. regimen.

In statistical terms, H_1 : $\mu_1 = \mu_0$, H_{A1} : $\mu_1 \neq \mu_0$, i.e.,

H₁: secukinumab 300 mg s.c. regimen is not different to placebo regimen with respect to the mean change from BSL in the WORC PSD score at Week 16

The primary analysis will be conducted via mixed-effects model repeated measures (MMRM) which is valid under the missing at random (MAR) assumption. Treatment group, stratification factor (tear status) and analysis visit will be included as categorical factors and BSL WORC PSD score and BSL weight as continuous covariates. Treatment by analysis visit and BSL WORC PSD score by analysis visit will be included as interaction terms in the model. An unstructured covariance structure will be assumed for the model.

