#### 1 Introduction

The scope of this plan includes the primary and secondary analyses. The purpose of this amendment is to modify the analysis plan to reflect the early termination status of the study. At the time of termination, 21 patients had been randomized and 2 patients had completed the study. Patients who were screened by May 7, 2024 were permitted to continue in the study per protocol to study completion.

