#### 2 Statistical methods

## 2.1 Data analysis general information

The data will be analyzed by Novartis and/or a designated clinical research organization (CRO). Any data analysis carried out independently by the investigator should be submitted to Novartis before publication or presentation.

Summary statistics for continuous variables will include the number of participants (N), mean, standard deviation (SD), minimum, lower quartile, median, upper quartile and maximum. Summary statistics for discrete variables will be presented in the number and percent of participants in each category.

Missing values will not be imputed and are not included in calculations of summary statistics.

Efficacy and safety data for the 16-week placebo-controlled period or the entire study as appropriate will be presented by the following two treatment groups:

- Secukinumab 300 mg regimen
- Placebo regimen

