#### 5.4 Statistical models

#### 5.4.1 Summary statistics for binary and categorical data

Summary statistics for discrete variables will be presented in contingency tables and will include count and frequency in each category. If applicable, confidence intervals will be derived as well based on the score method including continuity correction (Newcombe 1998):

With z as  $(1-\alpha/2)$ -quantile of the standard normal distribution (SAS:  $z = probit(1-\alpha/2)$ , n as total number of participants (i.e., number of participants in the denominator), p as estimated crude incidence (number of participants with event / n) and q = 1-p

Then the lower limit is

$$L = 100 \times \max \left(0, \frac{2np + z^2 - 1 - z\sqrt{z^2 - 2 - \frac{1}{n} + 4p(nq + 1)}}{2(n + z^2)}\right)$$

and the upper limit is

$$U = 100 \times \min \left( 1, \frac{2np + z^2 + 1 + z\sqrt{z^2 + 2 - \frac{1}{n} + 4p(nq - 1)}}{2(n + z^2)} \right).$$

In addition, if L > p then L = p and if U < p then U = p.

For binary response variables the placebo-adjusted response rates including 95% confidence interval will be derived.

SAS code for risk difference:

proc freq data=;

tables response\* treatment / riskdiff;

run

Note the response value should be sorted with '1' ahead of '0'.

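### The amended SAP never presents the primary summary measure, the difference in mean WORC PSD change, or an interval for it; a baseline-adjusted difference with a 95% CI and no p-value would be a cheap addition

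*SAP*

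**What the plan says.** Protocol 3.1 defines the primary estimand with "Summary measure: difference in means between treatments". Protocol 9.3.3 estimates it with a repeated-measures model that includes tear status, and "BSL WORC PSD score and BSL weight as continuous covariates".

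The amended SAP makes the primary and secondary analyses descriptive because the study stopped early. For the primary endpoint, 2.5.2 states: "WORC PSD change from baseline over time will be presented by treatment group using a summary table. Superiority testing will be omitted". SAP 2.6.2 treats the PROMIS score the same way. SAP 2.1 gives the content of such tables: "Summary statistics for continuous variables will include the number of participants (N), mean, standard deviation (SD), minimum, lower quartile, median, upper quartile and maximum". On missing data it adds: "Missing values will not be imputed and are not included in calculations of summary statistics".

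For binary responses, SAP 5.4.1 goes further: "For binary response variables the placebo-adjusted response rates including 95% confidence interval will be derived". Continuous endpoints have no counterpart to this.

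On size, SAP section 1 reports: "At the time of termination, 21 patients had been randomized and 2 patients had completed the study". It continues: "Patients who were screened by May 7, 2024 were permitted to continue in the study per protocol to study completion".

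SAP section 4 attributes the changes to early termination. It neither restates nor withdraws the estimand, and SAP Table 1-1 still words the primary objective as a comparison with placebo.

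**The concern.** A superiority test and an effect estimate are separate things, and the amendment removes both for the continuous endpoints. A reader of the report will see two columns of mean change and subtract one from the other by eye. Nothing in the table shows how uncertain that subtraction is.

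The subtraction also carries any chance difference in baseline PSD. The raw difference in change is unbiased over repeated randomisations. Given an observed baseline gap, however, it is biased whenever change depends on baseline. Some negative dependence is plausible, because inclusion criterion 5 selects on a low WORC total score at Screening and Baseline, which invites regression to the mean. SAP 2.3.2 tabulates baseline PSD by arm, so a reader could see an imbalance but could not correct for it.

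At stake is how completely and readably a stopped trial is reported. No confirmatory claim depends on it.

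**Working it through.** **Inputs.** Planned size 117 per arm, difference 14, SD 30, two-sided 5% (SAP 3.1, Protocol 9.9.1). Randomised at termination: 21 (SAP section 1), taken as 10 v 11 under 1:1 allocation. The documents give neither the SD of baseline PSD nor the slope of change on baseline. Both are assumed here: SD 15 (range 12 to 18) and slope -0.5 (range -0.3 to -0.7).

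**1. The plan's own power.** SE = 30 x sqrt(2/117) = 3.92. Then 14/3.92 = 3.57, and 3.57 - 1.96 = 1.61, which gives power of 94.6%. The stated figure of about 95% is reproduced.

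**2. Precision at the size reached.** sqrt(1/10 + 1/11) = 0.437, so SE = 30 x 0.437 = 13.1. With t(19) = 2.093 the 95% half-width is 27.4 points, against 7.7 at 117 per arm. At SD 25 it is 22.9. Power for 14 points is about 17%. If the final size were 15 or 20 per arm, the half-width at SD 30 would be 22.4 or 19.2. If only 8 per arm had data, it would be 32.2.

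**3. Chance baseline imbalance.** In baseline-SD units its standard error is 0.437 at 10 v 11, a 95% range of +/-0.86, against 0.13 (+/-0.26) as planned. The probability of a gap above 0.5 SD is 25% at 10 v 11, 17% at 15 per arm, 11% at 20 per arm and under 0.1% at 117 per arm.

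**4. What imbalance does to the raw difference, and what adjustment does to the interval.**
- Shift SD = slope x baseline SD x 0.437.
- Implied correlation of baseline with change = slope x baseline SD / 30. Its square is the share of the variance of the difference that imbalance explains.
- Adjusted half-width = t(18) x 30 x 0.437 x sqrt(1 - r^2) x sqrt(1 + 1/17) = 28.3 x sqrt(1 - r^2). The last factor is the cost of estimating one slope.

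| Baseline SD, slope | Shift SD (95% range) | Implied r (absolute) | Share of variance | Adjusted half-width |
|---|---|---|---|---|
| 12, -0.3 | 1.6 (+/-3.1) | 0.12 | 1.4% | 28.1 |
| 15, -0.5 | 3.3 (+/-6.4) | 0.25 | 6% | 27.4 |
| 18, -0.7 | 5.5 (+/-10.8) | 0.42 | 18% | 25.7 |

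The unadjusted half-width is 27.4, so adjustment breaks even at a correlation of about 0.25. At 0.3 the adjusted half-width is 27.0, at 0.5 it is 24.5 and at 0.7 it is 20.2. The last two correlations lie outside what the assumed slopes and SDs imply.

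**The case against.** The strongest reply is that the change is deliberate and declared, and that little is lost.

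- **The table is enough to rebuild the contrast.** N, mean and SD by arm allow anyone to compute the unadjusted difference and its interval. This stands. What cannot be recovered is the adjusted estimate.
- **The comparison with binary endpoints is weak.** SAP 5.4.1 is generic appendix text. SAP 2.6.2 promises only frequency tables for categorical endpoints, and section 5 is not among the sections listed as changed in the May 2024 update. The line may be a leftover. This stands in part: the line shows that an interval without a test fits the SAP's idea of description, but it does not prove that the sponsor chose to treat the endpoints unequally.
- **A modelled effect from a design meant to be confirmatory may be over-read.** This is a real cost. It calls for a clear label, and the width of the interval itself warns the reader.

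A reader might also draw three stronger conclusions, which the documents do not support:

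- *Adjustment would sharpen the estimate.* Under the assumed slopes and SDs the half-width runs from slightly worse than unadjusted to less than 2 points better.
- *Imbalance could by itself create or hide the planned effect.* Setting +/-6.4 against 14 suggests this, but the proper yardstick is total noise of about +/-27, of which imbalance is a small part.
- *The estimate is needed for pooling with the companion study.* Protocol 9.4.1 tests the two studies separately, neither document contains a pooling plan, and by-arm N, mean and SD already allow mean differences to be combined.

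**Conclusion.** The point holds as a low-severity reporting gap. The SAP's planned output for the continuous endpoints contains neither the protocol's primary summary measure nor its uncertainty, although the decision not to test does not require that omission. The difference would carry a 95% half-width of about 27 points at 10 v 11 and SD 30. Stating this is more informative than two bare means.

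Adjustment for baseline PSD is justified because it removes conditional bias from an imbalance that is seen. That bias has an SD of about 1.6 to 5.5 points, against a total standard error of about 13. No gain in precision should be claimed unless the correlation of baseline with change is clearly above 0.3.

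These sizes rest on the assumed baseline SD and slope, and on 21 patients. Patients already screened could still enter, so the final number may be higher; with no imputation, the number with Week 16 data may be lower. Imbalance remains material at 15 to 20 per arm. Nothing here argues for restoring the superiority test or the full repeated-measures model.

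**What to change.** Keep the summary tables and the omission of testing. Add to SAP 2.5.2 a sentence to this effect: the difference in mean change in WORC PSD at Week 16, and at Week 24, will be estimated in the FAS from observed values by ANCOVA on treatment and baseline WORC PSD, and reported with a 95% CI, no p-value and a label stating that it is descriptive estimation only. Tear status may be added if numbers allow, under a rule fixed before unblinding, since each further term costs a degree of freedom. Put the matching sentence for the PROMIS score in 2.6.2, with its own baseline as covariate. State in 5.4.1 whether the binary-response line still applies, so that the two endpoint types are handled on the same footing.

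The cost is one table row per endpoint and time point and a few lines of code, using a baseline score already collected. The downside is a very wide interval that could be over-read, which is why the label matters.

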#### 2.5.3 Handling of missing values

Missing values will not be imputed.

#### 2.5.4 Sensitivity analyses

No sensitivity analyses are planned.

## 2.6 Analysis supporting secondary objectives

Due to the premature study discontinuation, purely descriptive analyses will be performed for secondary endpoints. Analysis on secondary endpoints will be done based on FAS.

#### 2.6.1 Secondary endpoint(s)

The secondary efficacy variables include:

- Proportion of participants who achieve an improvement (increase) of at least 40 points from BSL in WORC PSD at Week 16
- Proportion of participants who achieve an improvement (increase) of at least 50 points from BSL in the WORC total score at Week 16
- Change from BSL in PROMIS SF UE score at Week 16

- Proportion of participants who achieve an improvement (increase) of at least 40 points from BSL in WORC PSD at Week 24
- Change from BSL in WORC PSD score at Week 24

## 2.6.2 Statistical hypothesis, model, and method of analysis

The secondary objectives will be analyzed in a purely descriptive manner. Categorical variables will be presented in frequency tables. PROMIS change from baseline over time will be presented by treatment group using a summary table. No testing strategy will be applied.

## 2.6.3 Handling of missing values

Missing values of secondary endpoints will not be imputed.

## 2.6.4 Sensitivity analyses

Not applicable.

## 2.6.5 Supplementary analyses

Not applicable.

## 2.7 Safety analyses

All safety analyses will be based on the SAF and performed on treatment received or actual treatment as described below:

The actual treatment or treatment received for summaries of safety data will differ to the treatment assigned at randomization only if a participant received the wrong treatment during the entire study.

For those participants who did not receive the randomized treatment, i.e., who received erroneously the wrong treatment at least once, an additional AE listing will be prepared displaying which events occurred after the treatment errors.

Safety summaries will include only data from the on-treatment period except for baseline data which will also be summarized where appropriate (e.g., change from baseline summaries). In addition, a separate summary for death including on treatment and post treatment deaths will be provided. In particular, summary tables for adverse events (AEs) will summarize only on-treatment events, with a start date during the on-treatment period (treatment-emergent AEs).

The on-treatment period lasts from the date of first administration of study treatment up to last administration + 84 days.

#### 2.7.1 Adverse events (AEs)

All information obtained on adverse events will be displayed by treatment group and participant.

The number (and percentage) of participants with treatment emergent adverse events will be summarized in the following ways:

- by treatment, primary system organ class and preferred term.
- by treatment, primary system organ class, preferred term and maximum severity.

Confidence intervals for the crude rate will be derived as described in Section 5.4.

Treatment emergent adverse events are defined as events started on or after the first dose of study medication or events present prior to the first dose of study medication but increased in severity on or after dosing based on preferred term and within last dose + 84 days (inclusive).

A participant with multiple adverse events within a primary system organ class is only counted once towards the total of the primary system organ class.

Separate summaries will be provided for study treatment related adverse events, death, serious adverse event, other significant adverse events leading to discontinuation and adverse events leading to dose adjustment or interruption.

Adverse events reported will be presented in descending frequency according to its incidence in the AIN457 300 mg group starting from the most common event. AEs will be summarized by presenting the number and percentage of participants having any AE, having an AE in each primary system organ class and having each individual AE (preferred term).

Summaries will also be presented for AEs by severity and for study treatment related AEs. If a particular AE 'severity' is missing, this variable will be listed as missing and treated as missing in summaries. If a participant reported more than one adverse event with the same preferred term, the adverse event with the greatest severity will be presented. If a participant reported more than one adverse event within the same primary system organ class, the participant will be counted only once with the greatest severity at the system organ class level, where applicable. Of note, AEs by severity will be provided by SOC in the study report and AEs by severity and PTs may be provided if required at ad-hoc basis.

The MedDRA version (version 27.0 or above) used for reporting the study will be described in a footnote.

In addition, exposure time-adjusted incidence rates including 95% confidence intervals will be provided for the entire study period following the guideline as below:

- Primary SOC level for AE and SAE
- RMP risks
- PT level for SAE
- Overall PT level for AE and SAE
- Other selected AEs on lower levels (e.g., PT), if appropriate

Algorithms for date imputations are provided in Section 5.1.2.

Non-treatment emergent adverse events will be flagged on the overall AE listing. These adverse events occurred before the first dose of the study treatment or after 84 days post the last dose.

An overview of the safety analyses (i.e., crude incidence, exposure time-adjusted incidence) which will be performed for adverse events and other binary safety variables (e.g., labs and vital signs) for each analysis period is described in Table 2-3.

Table 2-3	Overview of analyses on some safety endpoints								
Analysis period	AEs & SAEs	RMP risks	AEs by severity	Study drug related AEs	Notables (vitals/lab)				
Entire Study	

crude incidence

	
 
crude incidence
 
	
 
crude incidence
 
	

crude incidence

	

crude incidence

				
	
 
exposure time adjusted incidence
 
	
 
exposure time adjusted incidence
 
							

Table 2-3 Overview of analyses on some safety endpoints

For the legal requirements of ClinicalTrials.gov and EudraCT, two required tables on **ontreatment/treatment emergent** adverse events which are not serious adverse events with an incidence greater than z% and on **on-treatment/treatment emergent** serious adverse events and SAE suspected to be related to study treatment will be provided by system organ class and preferred term on the safety set population. Here threshold value z is set to 2 (%) but it may be updated following review of the dry run outputs.

If for a same participant, several consecutive AEs (irrespective of study treatment causality, seriousness and severity) occurred with the same SOC and PT:

- a single occurrence will be counted if there is  $\leq 1$  day gap between the end date of the preceding AE and the start date of the consecutive AE
- more than one occurrence will be counted if there is > 1 day gap between the end date of the preceding AE and the start date of the consecutive AE

For occurrence, the presence of at least one SAE/SAE suspected to be related to study treatment/non SAE has to be checked in a block e.g., among AEs in a  $\leq$  1 day gap block, if at least one SAE is occurring, then one occurrence is calculated for that SAE.

The number of deaths resulting from SAEs suspected to be related to study treatment and SAEs irrespective of study treatment relationship will be provided by SOC and PT.

A listing of participants with anaphylaxis (including signs and symptoms) will be provided.

#### 2.7.2 **Deaths**

Separate summary and listing will be provided for deaths.

#### 2.7.3 Laboratory data

Laboratory data will be listed by treatment group, participant, and visit/time and if normal ranges are available abnormalities will be flagged. Summary statistics will be provided by treatment and visit/time.

The general guideline for laboratory summaries (including Vital signs in Section 2.7.4.1) are as below:

- All the summary of lab outputs (newly occurring notables, maximum changes, by visit summary statistics) will consider the "on-treatment" data. i.e., all assessments up to last dose + 84 days.
- All records are displayed in the listing with the on-treatment flag. i.e., occurred up to last dose + 84 days- yes or no, as well as eCRF visits and epoch.

The summary of laboratory evaluations will be presented for two groups of laboratory tests (hematology and clinical chemistry).

Descriptive summary statistics for the change from baseline to each study visit will be presented. These descriptive summaries will be presented by laboratory test and treatment group. Change from baseline will only be summarized for participants with both baseline and post baseline values and will be calculated as:

change from baseline = post baseline value – baseline value

For laboratory test values below Lower Level of Quantification (LLQ) or above Upper Level of Quantification (ULQ) (i.e., numeric part is missing in the database) will be imputed as LLQ or ULQ value, respectively. These laboratory values will be displayed in listings using the standard unit with the reported sign ("<" or ">").

For each parameter, the maximum change (maximum decrease and maximum increase) from baseline within treatment period will be analyzed analogously.

The following laboratory parameters will be analyzed with respect to numerical Common Terminology Criteria for Adverse Events (CTCAE) grades, given in Table 2-4: hemoglobin, platelets, white blood cell count, neutrophils, lymphocytes, creatinine, total bilirubin (TBL), alanine aminotransferase (ALT), aspartate aminotransferase (AST), alkaline phosphatase (ALP), glucose.

Table 2-4 CTCAE (v4.03) grades for laboratory parameters to be analyzed

	· , o		•	
CTCAE v4.03 Term	Grade 1	Grade 2	Grade 3	Grade 4
HGB decreased (Anemia)	<lln 100="" g="" l<="" td="" –=""><100 – 80 g/L	<80 g/L	See Note 1 below	</lln>	<100 – 80 g/L	<80 g/L	See Note 1 below
Platelet count decreased	<lln -="" 75.0="" ×10e9
/L</lln>	<75.0 - 50.0 ×10e9 /L	<50.0 - 25.0 ×10e9 /L	<25.0 × 10e9 /L
White blood cell decreased	<lln -="" 10e9
/L</lln>	<3.0 - 2.0 × 10e9 /L	<2.0 - 1.0 × 10e9 /L	; <1.0 × 10e9 /L
Neutrophil count decreased	<lln -="" 1.5="" 10e9
/L</lln>	<1.5 - 1.0 × 10e9 /L	<1.0 - 0.5 × 10e9 /L	<0.5 × 10e9 /L
Lymphocyte count decreased	<lln -="" 0.8="" ×
10e9/L</lln>	<0.8 - 0.5 × 10e9 /L	<0.5 - 0.2 × 10e9 /L	<0.2 × 10e9 /L
Creatinine increased	>ULN - 1.5 × ULN	>1.5 - 3.0 × ULN	>3.0 - 6.0 × ULN	>6.0 × ULN
TBL increased	>ULN - 1.5 × ULN	>1.5 - 3.0 × ULN	>3.0 - 10.0 × ULN	>10.0 × ULN
GGT increased	>ULN - 2.5 × ULN	>2.5 - 5.0 × ULN	>5.0 - 20.0 × ULN	>20.0 × ULN
ALT increased	>ULN - 3.0 × ULN	>3.0 - 5.0 × ULN	>5.0 - 20.0 × ULN	>20.0 × ULN
AST increased	>ULN - 3.0 × ULN	>3.0 - 5.0 × ULN	>5.0 - 20.0 × ULN	>20.0 × ULN
ALP increased	>ULN - 2.5 × ULN	>2.5 - 5.0 × ULN	>5.0 - 20.0 × ULN	>20.0 × ULN
Glucose increased (Hyperglycemia)	>ULN - 8.9 mmol/L	>8.9 - 13.9 mmol/L	>13.9 - 27.8 mmol/L	>27.8 mmol/L
	>ULN - 7.75	>7.75 - 10.34	>10.34 - 12.92	
Cholesterol high	mmol/L	mmol/L	mmol/L	>12.92 mmol/L
Hypertriglyceridemia	1.71 - 3.42 mmol/L	>3.42 - 5.7mmol/L	>5.7 - 11.4 mmol/L	>11.4 mmol/L

Note 1: Grade 4 Hemoglobin events are defined as life-threatening anemia events and will not be displayed in the table, as a numerical range is not provided in the CTCAE.

Of note, baseline will be defined as last assessment prior to first dose. Participants with abnormal laboratory values will be listed and values outside the normal ranges will be flagged.

The number and percentage of participants with clinically CTCAE grade newly occurring or worsening after baseline (treatment emergent) will be presented. Absolute and relative frequencies will be derived for non-overlap groups: CTCAE grade 1, CTCAE grade 2, CTCAE grade 3, and CTCAE grade 4.

Newly occurring or worsening liver enzyme abnormalities will also be summarized (crude incidence as described in above, including 95% confidence intervals) based on the event criteria given in Table 2-5:

Table 2-5 Liver-related events

Parameter	Criterion
ALT	>3×ULN; >5×ULN; >8×ULN;>10×ULN, >20×ULN
AST	>3×ULN; >5×ULN; >8×ULN >10×ULN; >20×ULN
ALT or AST	>3×ULN; >5×ULN; >8×ULN >10×ULN; >20×ULN
TBL	>1.5×ULN, >2×ULN, >3×ULN,
ALP	>2×ULN, >2.5×ULN, >3×ULN. >5×ULN
ALT or AST & TBL	ALT or AST>3×ULN & TBL >2×ULN;
	ALT or AST >5×ULN & TBL >2×ULN;
	ALT or AST >8×ULN & TBL >2×ULN;
	ALT or AST >10×ULN & TBL >2×ULN
ALP & TBL	ALP >3×ULN & TBL >2×ULN
	ALP >5×ULN & TBL >2×ULN
ALT or AST & TBL & ALP	ALT or AST>3×ULN & TBL >2×ULN & ALP ≤2×ULN (Hy's Law)
	Note: elevated ALP may suggest obstruction as a consequence of gall bladder or bile duct disease; ALP may also be increased in malignancy. FDA therefore terms Hy's Law cases as indicators of pure hepatocellular injury . This does not mean that cases of ALT or AST >3×ULN & TBL >2×ULN & ALP >2×ULN may not result in severe DILI.

For a combined criterion to be fulfilled, all conditions have to be fulfilled on the same visit. The criteria are not mutually exclusive, e.g., a participant with ALT =  $6.42 \times ULN$  is counted for ALT >  $3 \times ULN$  and ALT>  $5 \times ULN$ .

Individual participant data listings will be provided for participants with newly occurring or worsening abnormal laboratory data. Data of participants with newly occurring or worsening liver enzyme abnormalities or renal abnormalities (as defined in the protocol) will be listed in an additional listing.

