#### **Study Period 2 (Follow up period)**

A follow-up period (Study period 2) of 8 weeks after the end of the treatment period is planned to assess the maintenance of effect and collect follow-up safety data up to Week 24.

Participants should continue on stable NSAID therapy and physiotherapy during this period. Reduction in NSAID dose is permitted, but participants must not increase above dose established during run-in. Corticosteroid injections are also not permitted after Week 16.

Placebo dose

[figure not shown]

Figure 1-1 Study Design

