## 2.7.4 Other safety data

#### **2.7.4.1 Vital signs**

The summary of vital signs will only include treatment emergent data, which are defined as those vital sign measurements after the first dose of study treatment and up to last dose + 84 days.

Analysis in vital sign measurement using descriptive summary statistics for the change from baseline for each post-baseline visit will be performed. These descriptive summaries will be

presented by vital sign and treatment group. Change from baseline will only be summarized for participants with both baseline and post-baseline values and will be calculated as:

change from baseline = post-baseline value – baseline value

The number and percentage of participants with newly occurring notable vital signs will be presented. Criteria for notable vital sign abnormalities are provided in Table 2-6:

Table 2-6 Criteria for notable vital sign abnormalities

Vital sign (unit)	Notable abnormalities	
Systolic blood pressure (mmHg)	>= 140 mmHg or < 90 mmHg	
Diastolic blood pressure (mmHg)	>=90 mmHg or <60 mmHg	
Pulse (bpm)	> 100 bpm or <60 bpm	

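### Should laboratory and vital-sign summaries allow grace days beyond last dose + 84 days, so that a slightly late Week 24 result is counted?

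*SAP*

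**What the plan says.** SAP 2.7.3 bases all laboratory summaries on "all assessments up to last dose + 84 days" and says that the same guideline covers vital signs. SAP 2.7.4.1 repeats it: the vital-sign summary takes "those vital sign measurements after the first dose of study treatment and up to last dose + 84 days". SAP 2.1.1.4, SAP 2.7 and Protocol 9.4.2 give the same 84-day on-treatment period for safety data in general.

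Later results are not discarded. SAP 2.7.3 states: "All records are displayed in the listing with the on-treatment flag". The number and percentage of participants with a CTCAE grade "newly occurring or worsening after baseline (treatment emergent) will be presented", and in addition "Individual participant data listings will be provided for participants with newly occurring or worsening abnormal laboratory data".

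On timing, Protocol 1.3 sets no numerical visit window and asks only that visits be as near to the planned day as can be managed. Protocol 6.5 keeps the schedule counted from baseline whatever happens to dosing. SAP 1.1 describes the follow-up period as "planned to assess the maintenance of effect and collect follow-up safety data up to Week 24".

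**The concern.** Two clocks run side by side. Visits are fixed to baseline, while the cut-off moves with the actual last dose. For a participant dosed on schedule they meet exactly at Week 24, so a one-day slip decides whether the last planned safety sample is counted. SAP Table 2-1 maps assessments up to Day 183 to Week 24, so a Day 172 vital-sign result would be labelled Week 24 and then left out of the Week 24 summary. That looks like an oversight, given that the follow-up period exists partly to gather safety data to Week 24.

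Chemistry and hematology are most exposed, because Protocol Table 1-2 schedules them only twice after baseline, at Weeks 16 and 24. A new abnormality in a late final sample would be absent from the by-visit, CTCAE and liver counts.

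**Working it through.** **1. Reproduce the plan's days.** SAP 2.1.1.2 counts the first dose as Day 1, so target day = 7 × week + 1. Week 12 = 85, Week 16 = 113 and Week 24 = 169. The half-spacing rule in SAP 2.4.1.1 gives the general Week 24 window as 169 − 14 + 1 = 156 to 169 + 14 = 183. For vital signs, where the previous visit is Week 16 (56 days earlier), the lower limit is 169 − 28 + 1 = 142. Both match Table 2-1.

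**2. The cut-off.** Cut-off day = last-dose day + 84, read as inclusive because SAP 2.7.1 says so for adverse events.

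| Last dose | Cut-off | Day 169 result | Day 170 result |
|---|---|---|---|
| Day 84 | 168 | out | out |
| Day 85 | 169 | in | out |
| Day 86 | 170 | in | in |

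If the dose and the visit are late by the same amount, nothing is lost.

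**3. What one late visit costs.**
- Scheduled post-baseline laboratory days are 113 and 169, so 1 of 2 is lost.
- Scheduled post-baseline vital-sign days are 15, 29, 57, 85, 113 and 169, so 1 of 6 is lost.

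**4. Window days past the cut-off (Day 85 dose).** Days 170 to 183 are 14 days: 14 of 28 in the general window (156–183) and 14 of 42 in the vital-sign window (142–183). The laboratory group is not legible in the public copy, so the general column stands in for it. These are days available for labelling and say nothing about how many visits fall there.

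**5. The natural alternative.** Adding the 14-day upper half-width (183 − 169) gives last dose + 98 days.

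| Last dose (nominal day) | + 84 | + 98 |
|---|---|---|
| Baseline (1) | 85 | 99 |
| Week 1 (8) | 92 | 106 |
| Week 2 (15) | 99 | 113 |
| Week 3 (22) | 106 | 120 |
| Week 4 (29) | 113 | 127 |
| Week 8 (57) | 141 | 155 |
| Week 12 (85) | 169 | 183 |

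Completers gain 14 days. Among participants who stop early but keep to the schedule, Day 113 results newly enter for those last dosed on Day 15 (113 − 15 = 98 days) and Day 22 (113 − 22 = 91 days). For the Day 15 stopper the new limit lands exactly on Day 113, so a zero-slack edge appears there. A participant last dosed on Day 57 has a Week 24 sample 169 − 57 = 112 days later, which is out under either rule.

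**6. Maximum change.** SAP 2.7.3 places this output under the on-treatment rule in one sentence and within the treatment period in another. Protocol 6.1.3 describes the treatment period as 16 weeks. On the narrower reading, Week 24 is outside that output whether late or not, so it is not a clear loss.

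**The case for a change.** The strongest case for a change is that the SAP plainly expects late visits. Its own example in 2.4.1.1 is a Week 4 visit held on Day 46, and it builds windows to keep such data usable, yet it gives the safety cut-off no tolerance. The same edge meets participants who stop early and decline further visits, because Protocol 7.1 sets their closing visit 12 weeks after the last dose. It also meets a Week 4 stopper at Week 16 (29 + 84 = 113). In a small trial a single result counts: if the 21 randomized at termination split about evenly, one participant is 1/10.5, or roughly 9.5% of an arm. Table 2-3 gives laboratory and vital-sign notables as crude incidence only, so a wider window would not disturb any exposure denominator.

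The arithmetic and the absence of tolerance stand. The inference that this is a defect does not:

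- Table 2-1 decides which visit label a record carries. It does not decide whether the record is on-treatment. A labelling rule and an on-treatment filter can coexist.
- The follow-up aim in SAP 1.1 concerns collecting data. The data are collected and listed. Protocol 9.4.2 separately confines the summaries to the on-treatment period.
- The 84 days also match the 12-week adverse-event monitoring minimum (Protocol 8.6.1), the SAE reporting period (8.6.3) and the early stoppers' closing visit (7.1). The alignment looks intended.

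**Conclusion.** No change is needed. The rule is determinate and consistent between protocol and SAP. A hard on-treatment limit that coincides with the last planned visit is a fair trade-off.

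Moving it to 98 days would exchange one sharp edge for another. It would depart from Protocol 9.4.2, using a limit that appears nowhere in the documents as a safety period. It would also split the safety windows: an abnormality 90 days after the last dose could enter a laboratory table, while an adverse event starting that day would not be treatment-emergent.

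The size is small. For an affected completer it is one of two scheduled laboratory samples or one of six vital-sign visits, missing from summary counts but present in flagged listings. Laboratory abnormalities that are new or worsening are also listed individually. SAP Section 1 records: "At the time of termination, 21 patients had been randomized and 2 patients had completed the study". Primary and secondary endpoints are to be analysed descriptively only, so no formal conclusion depends on these counts. If late Week 24 samples do occur, an analyst can report their number in a table footnote without altering any rule. The two phrases for maximum change are a wording slip that programming will settle.

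This rests on reading the 84-day limit as inclusive and on a Week 12 last dose at Day 85. Final enrolment may exceed 21, since patients already screened by the stated date could continue. The documents do not give actual visit dates, so the number of late Week 24 visits is unknown.
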